**Change History:**

Table numbers were updated.

Table 14.4.2 Summary of Concomitant Medications was added.

No other changes were made to the statistical methods.

**2. LIST OF ABBREVIATIONS AND DEFINITIONS OF TERMS**

AE	Adverse event
AUC 0-24	Area Under the plasma Concentration-time curve from Hour 0 to Hour 24
AUC 0-∞	Area Under the plasma Concentration-time curve from Hour 0 extrapolated to infinity
CN	Clear Nail
C max	maximum observed plasma concentration
CRF	Case report form
DSO	Distal subungual onychomycosis
MedDRA	Medical Dictionary for Regulatory Affairs
λ Z	elimination rate constant
LTR	Local Tolerability Reactions
N	Sample size
PK	Pharmacokinetic
SAE	Serious adverse event
SD	Standard deviation
t ½	elimination half-life
TEAE	Treatment-emergent adverse event
TGT	Target great toenail
T max	time to maximum observed plasma concentration
UPT	Urine Pregnancy Test
WHO	World Health Organization

### 3. INTRODUCTION

KERYDIN® (tavaborole) topical solution, 5%, the first oxaborole antifungal agent, was approved by the Food and Drug Administration for the topical treatment of onychomycosis of the toenails on 07 July 2014 (NDA 204427). This protocol is intended to satisfy the post-marketing study requirements (PMR-2154-1) and the Written Request of KERYDIN (tavaborole) topical solution, 5% in pediatric subjects with onychomycosis of the toenails.

### 4. STUDY OBJECTIVES

The primary objective of this study is to assess the safety and tolerability of KERYDIN (tavaborole) topical solution, 5% applied once daily for 48 weeks in pediatric subjects ages 6 to 16 years and 11 months with onychomycosis of the toenails.

The secondary objective is to perform PK assessments in a subgroup of at least 16 evaluable subjects ages 12 to 16 years and 11 months following topical administration under maximal use conditions.

### 5. INVESTIGATIONAL PLAN

#### 5.1 Overall Study Design

This is an open-label study to evaluate the safety, tolerability, and pharmacokinetics of KERYDIN (tavaborole) topical solution, 5% in treating distal subungal onychomycosis (DSO) of the toenail in pediatric subjects ages 6 to 16 years and 11 months. An eligible subject will have a target great toenail (TGT) with at least 20% involvement with a positive potassium hydroxide (KOH) wet mount and positive fungal culture for *T. rubrum* or *T. mentagrophytes* from a sample obtained from an affected great toenail during the Screening period. KOH and fungal culture will be sent to a central mycology laboratory for eligibility determination. Both great toenails can be sampled at Screening.

The mycological confirmation of eligibility will be performed as follows:

1. Initial sample is KOH (+) and culture (+) for *T. rubrum* or *T. mentagrophytes*, with or without co-infection with *Candida* spp. or *E. floccosum*, subject is eligible for enrollment within the maximum period of 10 weeks (i.e., within 70 days) from the Screening visit.
2. Initial sample is KOH (−) or initial sample is KOH (+) and culture (−): The sample may be repeated and will be assessed as follows:
  - If a repeat sample is KOH (+) and culture (+) for *T. rubrum* or *T. mentagrophytes* with or without co-infection with *Candida* spp. or *E. floccosum*, for enrollment as long as the subject is enrolled within the maximum period of 10 weeks (i.e., within 70 days) from the Screening visit.

Eligible subjects will apply KERYDIN (tavaborole) topical solution, 5% once daily to all affected toenails (the TGT as well as all other toenails identified by the Investigator at the Baseline visit as having the clinical characteristics of onychomycosis) throughout the 48-week treatment period.

Subjects will be evaluated at Screening, Baseline (Day 1), and at Weeks 2, 4, 8, 16, 24, 32, 40, 48, and 52. Each evaluation will include a clinical assessment of the adverse events (AEs) and local tolerability evaluation.

Additional procedures are performed as follows:

- Mycology sampling at Screening, Week 24, and Week 52/early termination (ET)
- Clinical disease severity of the TGT at Screening, Week 24, and Week 52/ET
- Safety laboratory testing at Baseline, Week 24, and Week 52/ET
- Digital photography at Screening, Week 24, and Week 52/ET
- Urine pregnancy tests (UPTs) will be performed on all postmenarchal females at all scheduled visits starting at the Baseline visit.

Subjects will start diaries at Baseline (Day 1) and will complete the diary as instructed.

In this study, there will be a PK subgroup of at least 16 evaluable subjects ages 12 to 16 years and 11 months studied under maximal use conditions. Subjects in this maximal use subgroup will apply the study drug on all 10 toenails, including up to 2 mm of the surrounding skin, for 28 days ( $\pm$ 7 days). On Day 15, a pre-dose PK sample will be collected to assess steady state trough level. On Day 29, the study drug application will be done at the study site, and PK samples will be collected prior to dosing, as well as 4, 6, 8, and 24 hours post-dose on Days 29-30. After PK sampling is complete, study drug will be applied only to the affected toenails.

### 5.1.1 Schedule of Visits and Assessments

Study Visit No.	1 (Screening)	2 (Baseline)	3	4	4a (PK)	5	6	7	8	9	10	11 (or ET)
Study Day (±7 days V4-11, +7 days V3)	Up to -70 days	1	15	29	30							
Study Week			2	4		8	16	24	32	40	48	52
Informed consent	x											
Obtain subject number	x											
Demographics	x											
Medical and medication history	x	x										
Abbreviated physical examination		x										
KOH mount and fungal culture c	x							x				x
Review inclusion/exclusion criteria	x	x										
Identify target great toenail (TGT)	x	x										
Identify 'other toes' to be treated		x										
Clinical assessment (% TGT disease severity)	x							x				x
Concomitant medications	x	x	x	x	x	x	x	x	x	x	x	x
Adverse events (AEs)	x	x	x	x	x	x	x	x	x	x	x	x
Safety laboratory tests		x					x					x
Urine pregnancy test (UPT) for postmenarchal females		x	x	x		x	x	x	x	x	x	x
Vital signs (blood pressure, pulse rate, respiratory rate) a	x	x	x	x		x	x	x	x	x	x	x
LTR assessment		x	x	x		x	x	x	x	x	x	x
PK subgroup sampling b			x	x	x b							
Photography of the TGT c	x						x					x
Weigh and dispense new study drug kit		x	x	x		x	x	x	x	x		
Study drug collection/weighing/accountability			x	x		x	x	x	x	x	x	x
Supervise study drug self-administration d		x	x	x		x	x	x	x	x		
Diary review and training/re-training		x	x	x		x	x	x	x	x	x	x
Schedule next visit	x	x	x	x		x	x	x	x	x	x	x

ET, early termination; KOH, potassium hydroxide; PK, pharmacokinetic; LTR, local tolerability reaction

a Vital signs conducted after subject is sitting or supine for at least 5 minutes.

b For subjects in the PK subgroup, at Visit 3 (Day 15) a pre-dose sample will be collected and Visit 4 (Day 29), PK samples will be collected prior to dosing, as well as 4, 6, and 8 hours post-dose. At Visit 4a (Day 30), the 24-hour post-dose sample is collected prior to dosing.

c Perform photography procedures before mycology procedures.

d Application occurs at the site on visit days. For PK subgroup participants, the application for Visit 3 (Day 15) and Visit 4a (Day 30) is to occur after the subject has had their PK specimen drawn.

## **5.2 Selection of Study Population**

### **5.2.1 Inclusion Criteria**

Subjects must meet all of the following inclusion criteria to be eligible for this study:

1. Male or female subjects, ages  $\geq$  6 years and  $\leq$  16 years and 11 months at the time of enrollment
2. Have a parent or guardian able to understand, to agree to, and to sign the study ICF; subject has the ability to give assent based on their age, maturity, and psychological state at the time of parental/guardian consent
3. A clinical diagnosis of DSO affecting either great toenail with positive KOH and *T. rubrum* or *T. mentagrophytes* culture from the TGT confirmed by a central mycology laboratory during the Screening period
4. DSO involving at least 20% of the TGT
5. TGT capable of growing, as assessed by the Investigator or qualified designee
6. Subject and parent/guardian (if applicable) are willing and able to comply with study drug instructions, comply with study instructions, and commit to attending all visits
7. Postmenarchal females must agree to use a medically accepted method of contraception for the entire study period

### **5.2.2 Exclusion Criteria**

Subjects who meet any of the following exclusion criteria will be excluded from entering the study:

1. One or more of the following conditions affecting the TGT:
  - Proximal subungual onychomycosis
  - Onychomycosis involving the lunula
  - Superficial white onychomycosis, dermatophytoma, exclusively lateral disease, or yellow/brown spikes
  - Screening culture results that demonstrate co-infection with *Scopulariopsis* spp., *Scytalidium* spp. or other nondermatophyte molds (exception: *Candida* spp. and *E. floccosum* are permitted)

2. Anatomic abnormalities of the toe(s) or toenail(s) to be treated including, but not limited to: genetic nail disorders, pigmentary disorders, onychogryphosis, trauma to the toenail(s) to be treated, or other abnormality that in the Investigator's opinion may interfere with clinical evaluation of the toenail(s) or would indicate that the subject is unlikely to respond to a topical treatment for DSO
3. Current or past history of chronic moccasin-type tinea pedis (involving the sides or dorsum of the foot)
4. Current or past history of psoriasis or lichen planus involving the skin, nails or mucous membranes
5. History of any significant chronic fungal disease other than onychomycosis (eg, chronic mucocutaneous candidiasis)
6. Known diagnosis of type I or type II diabetes
7. Concurrent use of or have used any of the following topical or systemic medications within the indicated timeframe prior to Screening:
  - Topical antifungals applied to the toenails: 2 weeks
  - Systemic corticosteroids (including intramuscular injections): 4 weeks
  - Systemic immunosuppressive agents: 4 weeks
  - Systemic antifungals for treatment of onychomycosis or with known activity against dermatophytes: 24 weeks
8. Any significant active or past medical condition which, in the Investigator's opinion, may expose the subject to unacceptable risk by study participation, confound the evaluation of treatment response or AEs, or interfere with the subject's ability to complete the study
9. History of any known immunodeficiency
10. Known to be allergic to the study drug or excipients in the study drug
11. History of drug or alcohol abuse (current or within the past 6 months)
12. Participated in any other trial of an investigational drug or device within 30 days prior to Screening or participation in a research study concurrent with this study

### **5.3 Treatments**

KERYDIN (tavaborole) topical solution, 5% will be applied topically once daily for 48 weeks.

## 5.4 Efficacy and Safety Variables

### 5.4.1 Efficacy Variables

The efficacy assessments are intended to assess compliance with treatment for the purposes of the safety assessment.

#### 5.4.1.1 Clinical Assessment of the Target Toenail Involvement

Clinical involvement of the TGT will be assessed at Screening and Weeks 24 and 52/ET using the following definitions of disease severity:

- **Completely CN:** no clinical evidence of onychomycosis as evidenced by normal toenail plate, no onycholysis, and no subungual hyperkeratosis
- **Almost CN:** no more than minimal evidence of onychomycosis as evidenced by toenail plate dystrophic or discolored  $\leq 5\%$  of the distal aspect, with minimally evident onycholysis and subungual hyperkeratosis
- **Mild onychomycosis:** onychomycosis as evidenced by toenail plate dystrophic or discolored  $> 5\%$  to  $\leq 20\%$  of the distal aspect, with clearly evident onycholysis and subungual hyperkeratosis
- **Moderate onychomycosis:** onychomycosis as evidenced by toenail plate dystrophic or discolored  $> 20\%$  to  $\leq 50\%$  of the distal aspect, with clearly evident onycholysis and subungual hyperkeratosis
- **Severe onychomycosis:** onychomycosis as evidenced by a toenail plate dystrophic or discolored  $> 50\%$  of the distal aspect, with pronounced onycholysis and subungual hyperkeratosis

#### 5.4.1.2 KOH Mount and Central Fungal Culture

Mycology sampling is to occur after all photography procedures for that visit have been completed. At Screening, the Investigator may perform a KOH wet mount at the study site to confirm the clinical diagnosis of onychomycosis prior to obtaining a sample for the central mycology laboratory; however, care must be taken to obtain sufficient subungual debris for the analysis at the central laboratory. The local KOH wet mount is an optional procedure and only the central mycology laboratory reading will be used for analysis and eligibility determination. If both great toenails are potentially eligible by clinical criteria, then both great toenails can be sampled at Screening. A subject that fails mycology criteria may be resampled.

A sample of subungual debris will be obtained again at Week 24 and Week 52/ET.

## **5.4.2 Pharmacokinetic Assessments**

Blood samples for the determination of plasma levels of tavaborole and PK parameters will be obtained under maximal use conditions (once daily application to all 10 toenails, including up to 2 mm of the surrounding skin) from the subgroup of subjects ages 12 to 16 years and 11 months to achieve at least 16 evaluable subjects. Subjects in the maximal use subgroup will apply the study drug on all 10 toenails, including up to 2 mm of the surrounding skin, for 28 days  $\pm$  7 days. At Visit 3 (Day 15) a pre-dose PK sample will be collected to assess steady state trough level. At Visit 4 (Day 29), the study drug application will be done at the study site, and PK samples will be collected prior to dosing, as well as 4, 6, and 8 hours post-dose. At Visit 4a (Day 30) the sample will be collected 24 hours post-dose and prior to the application for that day.

Approximately 24 mL of blood (6 samples, 4 mL each) will be taken from each of the 16 subjects for the PK determination.

## **5.4.3 Safety Variables**

### **5.4.3.1 Local Tolerability Reactions**

Safety evaluations will include local tolerability reactions (LTRs) (burning/stinging, induration/edema, oozing and crusting, pruritus, erythema, and scaling), as reported by the subject and/or evaluated by the Investigator at Baseline and each study visit thereafter. LTRs will be documented on the case report form (CRF) specifically designed to capture LTR information (local tolerability signs CRF) and not on the AE CRF. LTRs that require treatment (eg, with a concomitant medication or drug interruption or drug discontinuation) are an exception to this guideline; these LTRs should be documented on both the local tolerability signs CRF and on the AE CRF.

Grade	Guideline
Burning/Stinging	
0 - None	No stinging/burning
1 - Mild	Slight warm, tingling sensation; not really bothersome
2 - Moderate	Definite warm; tingling/stinging sensation that is somewhat bothersome
3 - Severe	Hot, tingling/stinging sensation that has caused definite discomfort
Induration/Edema	
0 - None	No elevation
1 - Mild	Barely perceptible elevation
2 - Moderate	Clearly perceptible elevation but not extensive
3 - Severe	Marked and extensive elevation
Oozing and Crusting	
0 - None	Absent
1 - Mild	Faint signs of oozing
2 - Moderate	Definite oozing or crust but with 5 or fewer sites per area
3 - Severe	Marked and extensive oozing and crusting
Pruritus	
0 - None	No pruritus
1 - Mild	Occasional, slight itching/scratching
2 - Moderate	Constant or intermittent itching/scratching which is not disturbing sleep
3 - Severe	Severe bothersome itching/scratching which is disturbing sleep
Erythema	
0 - None	No redness present
1 - Mild	Faintly detectable erythema; very light pink
2 - Moderate	Dull red, clearly distinguishable
3 - Severe	Deep/dark red
Scaling	
0 - None	No scaling
1 - Mild	Barely perceptible shedding, noticeable only on light scratching or rubbing
2 - Moderate	Obvious but not profuse scaling
3 - Severe	Heavy scale production

### 5.4.3.2      **Vital Signs**

Vital signs will be measured at each study visit after the subject has been sitting or supine for at least 5 minutes. Vital sign measurements taken will be blood pressure, pulse rate, and respiratory rate.

### 5.4.3.3      **Clinical Safety Laboratory Parameters and Pregnancy Tests**

Clinical safety laboratory parameters will be assessed at Baseline, Week 24, and Week 52/ET, if applicable. Laboratory tests may be repeated more often if clinically indicated. Blood samples may be taken with the subject in a non-fasting state.

All out-of-normal range laboratory values must be evaluated by the Investigator or subinvestigator as to whether they are clinically significant (i.e., require medical intervention or have clinical signs and/or symptoms). Abnormal clinical laboratory parameters that are considered clinically significant by the Investigator will be recorded on the AE CRF except Baseline visit. Clinically significant laboratory abnormalities noted from the Baseline visit will be recorded as medical history. The AE should be reported as a clinical diagnosis when possible. Laboratory tests will be performed by the central laboratory and are presented in Table 5.

UPTs will be performed at each scheduled visit on postmenarchal females starting at Baseline. If a UPT result is positive, the subject must be discontinued.

The Sponsor will designate a central laboratory for safety laboratory tests. All samples for clinical laboratory tests must be managed through the central laboratory designated by the Sponsor. Sample management (collection, storage, shipping, etc.) will be done according to the central laboratory instructions.

### **Safety Laboratory Parameters**

Hematology	Chemistry
Hemoglobin	Blood urea nitrogen
Hematocrit	Creatinine
Red blood cell count	Glucose (nonfasting)
Platelet count	Sodium, Potassium
White blood cell count	Aspartate aminotransferase, alanine aminotransferase
Neutrophils	Total bilirubin
Eosinophils	Alkaline phosphatase
Monocytes	Albumin
Basophils	Total protein
Lymphocytes	Urine pregnancy test (all scheduled visits starting at Baseline)

#### **5.4.3.4 Adverse Events**

An AE is any untoward medical occurrence or unintended change from the subject's Baseline (pretreatment) condition, including intercurrent illness, that occurs during a clinical trial after treatment has started, whether or not it is considered related to study treatment. An AE can therefore be any unfavorable and unintended sign (including an abnormal laboratory finding), symptom, or disease temporally associated with the use of an investigational product.

An AE is meant to include events that are either new or represent detectable exacerbations of preexisting conditions, and does not imply any judgment about causality.

AEs will be assessed at each visit. Any AE occurring on or after the date of the dose of study drug administration on Day 1 and up to and including the completion/termination date will be counted as treatment-emergent.

Adverse experiences may include but are not limited to subjective or objective symptoms spontaneously reported by the subject and/or observed by the Investigator or medical staff, including laboratory abnormalities of clinical significance. Preexisting conditions noted as part of the medical history at Screening must be reported on the appropriate medical history CRF page. Stable, ongoing conditions present at Screening should not be recorded as AEs if the severity at Screening remains unchanged during the study. However, preexisting conditions for which an increase in severity is observed after Screening must be recorded as AEs.

### **5.5 Statistical Methods**

All statistical processing will be performed using SAS® unless otherwise stated.

Descriptive statistics will include sample size, mean, median, standard deviation, minimum, and maximum continuous variables. Categorical variables will be tabulated with frequency counts and percentages.

#### **5.5.1 Disposition of Patients**

A tabulation of subject disposition will be provided. The tabulation will include the numbers of subjects who enter the study, complete the study, and discontinue the study. The reasons for discontinuation will be included.

#### **5.5.2 Data Sets Analyzed**

The following populations will be used:

- **Safety population:** all subjects who receive at least one confirmed dose of study drug and have at least one post-baseline safety assessment.

- **PK population:** all subjects from the maximal use subgroup with available PK data at Day 15 and at least one collection on Day 29.

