**5.5.7 Pharmacokinetics**

Pharmacokinetics will be tabulated for each collection day using descriptive statistics. Mean plasma concentrations will be plotted through time using both linear and semi-logarithmic scales. Plasma concentrations will also be plotted through time for each subject, using both linear and semi-logarithmic scales. Concentrations below the limit of quantitation will be set to zero for descriptive statistics.

The following PK parameters will be calculated for Day 15 (steady state trough level only) and Day 29 [steady state ( $\pm$ specified window)]:

- $C_{\max}$ : maximum observed plasma concentration
- $T_{\max}$ : time to maximum observed plasma concentration
- $AUC_{0-24}$ : area under the plasma concentration-time curve from Hour 0 to Hour 24, calculated using the linear trapezoidal rule
- $AUC_{0-\infty}$ : area under the plasma concentration-time curve extrapolated to infinity
- $\lambda_Z$ : elimination rate constant
- $t_{1/2}$ : elimination half-life

PK parameters will be calculated using actual sampling times.

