## **5.6 Changes in the Planned Analyses**

There are no changes to planned analyses. The PK population definition was clarified to include available PK data.

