Table 14.4.2: Summary of Concomitant Medications (Safety Population) .....	60
Table 14.4.4.1: Summary of Tavaborole Plasma Concentrations (PK Population) .....	61
Figure 14.4.4.1.1: Linear Plot of Mean Plasma Concentrations of Tavaborole by Time (PK Population) .....	62
Figure 14.4.4.1.2: Semi-logarithmic Plot of Mean Plasma Concentrations of Tavaborole by Time (PK Population) .....	63
Figure 14.4.4.1.3: By-Subject Linear Plots of Plasma Concentrations of Tavaborole by Time (PK Population) .....	64
Figure 14.4.4.1.4: By-Subject Semi-logarithmic Plots of Plasma Concentrations of Tavaborole by Time (PK Population) .....	65
Table 14.4.5.1: Summary of Pharmacokinetic Parameters of Tavaborole at Day 29 (PK Population) .....	66

Table 14.1.1.1: Summary of Subject Completion/Discontinuation

	KERYDIN® (N=xx)
Completed Study	
Yes	xx ( xx.x%)
No	xx ( xx.x%)
Reason for Discontinuation	
Adverse Event	xx ( xx.x%)
Lost to Follow-Up	xx ( xx.x%)
Pregnancy	xx ( xx.x%)
Protocol Deviation	xx ( xx.x%)
Withdrawal by Subject	xx ( xx.x%)
Other	xx ( xx.x%)

Listing 16.2.1.1

SOURCE: USERNAME\SPONSOR\PROJECT\JOBNAME (DATE,TIME)

Table 14.1.1.1.1: Summary of Subject Enrollment and Evaluability

KERYDIN®	
Number of Subjects Included in the Safety Population	xx
Number of Subjects Excluded from the Safety Population	xx
Reason for Exclusion from the Safety Population	
No Confirmed Dose of Study Drug	xx
No Post-Baseline Safety Assessment	xx
Number of Subjects Included in the Maximal Use Subgroup	xx
Number of Subjects Included in the PK Population	xx
Number of Subjects Excluded from the PK Population	xx
Reason for Exclusion from the PK Population	
Not Included in Maximal Use Subgroup	xx
No Available PK Data	xx

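### The PK population rule removes a complete Day 29-30 profile when only the Day 15 trough is missing, although no Day 29 parameter uses that trough

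*SAP*

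**What the plan says.** SAP section 5.5.2 sets the PK population as "all subjects from the maximal use subgroup with available PK data at Day 15 and at least one collection on Day 29".

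Section 5.1 gives the purpose of the earlier sample: "On Day 15, a pre-dose PK sample will be collected to assess steady state trough level". The main profile follows two weeks later, with a pre-dose sample and samples at 4, 6 and 8 hours on Day 29. The last point comes the next day: "At Visit 4a (Day 30) the sample will be collected 24 hours post-dose and prior to the application for that day".

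Section 5.5.7 states that parameters are "calculated for Day 15 (steady state trough level only) and Day 29". The listed parameters (Cmax, Tmax, the two AUCs, the elimination rate constant and the half-life) therefore belong to Day 29. Table 14.4.5.1 reports them under the PK population label. Table 14.4.4.1 and Figures 14.4.4.1.1 to 14.4.4.1.4 carry the same label.

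Table 14.1.1.1.1 offers two reasons for exclusion from the PK population: "Not Included in Maximal Use Subgroup" and "No Available PK Data". Section 5.6 adds that "The PK population definition was clarified to include available PK data".

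**The concern.** PK under maximal use is the study's secondary objective, and the Day 29-30 profile carries nearly all the information on it. The definition makes entry to every Day 29 PK summary depend on one sample taken two weeks earlier, which no Day 29 parameter uses. Observed data can therefore leave the summaries because a different visit was missed or a tube was lost.

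The rule also works in reverse. A subject with a valid Day 15 trough but no Day 29 sample is left out of the Day 15 column of Table 14.4.4.1, although that column needs nothing from Day 29.

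The subgroup is small, with a target of at least 16 evaluable subjects, so one or two avoidable exclusions are noticeable. What is at stake is completeness of a descriptive summary. No test or power calculation depends on it.

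**Working it through.** **Sample count (the plan's own figure).** Day 15 has 1 sample, Day 29 has 4 (pre-dose, 4, 6 and 8 h) and Day 30 has 1 (24 h). 1 + 4 + 1 = 6 samples, and 6 × 4 mL = 24 mL. This matches SAP section 5.4.2. The profile behind the Day 29 parameters is five of these six samples.

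**Applying the rule.**

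| Samples available | Day 15 condition | Day 29 condition | In PK population? | What is lost |
|---|---|---|---|---|
| All six | met | met | yes | nothing |
| All five of Day 29-30, no Day 15 | not met | met | no | the full Day 29-30 profile |
| Day 15 only | met | not met | no | the Day 15 trough |
| Day 15 plus one Day 29 sample at 4 h | met | met | yes | nothing |

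The second and fourth rows show the imbalance. A full profile is excluded, while a subject with a single post-dose sample is kept. The fourth row also shows that the rule does not secure a Day 15 versus Day 29 trough comparison, because it does not require the Day 29 pre-dose sample.

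**Illustrative size.** The SAP gives no rate of missing samples, so the rate p is an assumption. Take n = 16 maximal-use subjects with complete Day 29-30 profiles, each lacking the Day 15 sample independently with probability p.

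- Expected number excluded: 16p
- Chance that at least one is excluded: 1 − (1 − p)^16

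| p (assumed) | Expected excluded | Chance of at least one |
|---|---|---|
| 5% | 0.8 | 0.560 |
| 10% | 1.6 | 0.815 |
| 15% | 2.4 | 0.926 |

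Without the Day 15 condition, this loss from the Day 29 summaries is zero at any p.

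**Side remark on single samples.** The pre-dose draw is itself a Day 29 collection, so a subject with Day 15 plus that draw alone enters the population. Section 5.5.7 defines Tmax as "time to maximum observed plasma concentration" and sets no minimum number of samples. If the true peak is r times the trough (r assumed), a trough reported as Cmax understates that subject's Cmax by 1 − 1/r. With one such subject among 16 and otherwise equal values, the mean falls by (1 − 1/r)/16. For r = 1.5, 2 and 5 this is 2.1%, 3.1% and 5.0%. With r close to 1 the effect vanishes.

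**The case against.** The best defence is that the Day 15 trough supports steady state. Section 5.1 collects it for that purpose, and section 5.5.7 describes the Day 29 parameters as steady-state values. Requiring it also keeps one set of subjects for both days. Part of this stands: a common set is a legitimate aim, and the fix gives some of it up. But a missing sample is no evidence that steady state was not reached, the SAP makes no Day 29 parameter conditional on the Day 15 value, and the rule does not require the Day 29 pre-dose sample that the comparison would need.

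The clarification noted in section 5.6 does not help either, because the joint condition is still the wording of section 5.5.2.

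Four stronger readings are tempting but not supported:

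- **That the plan will report Cmax and Tmax from a lone pre-dose sample.** This is an inference from silence. Section 5.5.2 decides who enters the population, and Table 14.4.5.1 has a separate N for each parameter. The case needs the 4, 6, 8 and 24 h draws all to be lost, and the by-subject plots would expose it.
- **That Table 14.1.1.1.1 contradicts the definition.** Its second reason can be read as shorthand for failing the availability condition. It is terse and does not separate the causes, but it is not plainly wrong.
- **That eight outputs are damaged.** Eight carry the PK population label, but two of them (Tables 14.1.2.2 and 14.1.2.4) are demographic and baseline tables that only describe the population. The PK content affected is two tables and four figures.
- **That the target of 16 would be missed.** The SAP does not define evaluable. If it means membership of the PK population, exclusions would come from a larger group and the target could still be met.

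Excluded values may also still appear in Listings 16.2.6.3 and 16.2.6.4, which are not labelled as restricted.

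**Conclusion.** The concern holds for the Day 15 condition. As written, the definition removes observed Day 29-30 data from Tables 14.4.4.1 and 14.4.5.1 and the four PK figures when only the Day 15 sample is missing. It also removes a Day 15 trough when there is no Day 29 sample. This follows from the text and needs no assumed rate.

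The size does rest on assumptions. With 5% to 15% missing Day 15 samples, independent between subjects, 0.8 to 2.4 of 16 full profiles would be lost on average. The true figure could be zero. Nothing in the SAP shows that the remaining summary would be biased, only that it would rest on fewer subjects than have data.

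The single-sample Cmax and Tmax case is a minor remark: it is rare, has little effect on the mean, and is not something the SAP says will be done. Overall this is a cheap improvement to a descriptive secondary analysis and does not threaten the study's conclusions.

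**What to change.** In SAP section 5.5.2, separate the two days:

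1. Base Day 29 concentrations and parameters on maximal-use subjects with Day 29-30 data, without the Day 15 condition.
2. Summarise the Day 15 trough in all maximal-use subjects who have it.
3. Compare Day 15 and Day 29 troughs in subjects who have both samples.
4. Align the PK exclusion reasons in Table 14.1.1.1.1 with the revised rule, so that each excluded subject has a reason that fits.

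As a small addition to section 5.5.7, state that Cmax and Tmax are reported only for subjects with post-dose samples, with any minimum number set by the sponsor before analysis. Other subjects would appear in the concentration table only.

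The cost is an edit to one definition and one table shell, plus a sentence in section 5.5.7. Day 15 and Day 29 summaries may rest on slightly different subjects, so each needs its own N. The N for Cmax and Tmax could fall slightly. The wording may also need aligning with the protocol.
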